5 GENERAL CHARACTERISTICS

All analyses on general characteristics will be run on the ITT population, unless specified otherwise.

5.1 Subject Disposition

Subject disposition will be presented descriptively for the all screened population. This includes the number and percentage of subjects in each of the analysis populations defined in Section 4.1. A disposition summary by country and site and by time point will be given for the Intent-to-treat (ITT) population. The number and percentage of subjects who completed the trial and who prematurely discontinued will be summarized, along with the primary reasons for discontinuation.

A detailed list of tables and listings can be found in Section 14.1 and Section 16.1, respectively.

5.2 Protocol Deviations and Eligibility Criteria

A protocol deviation is any change, divergence, or departure from the study design or procedures defined in the protocol. Protocol deviations are considered as major if they can have an impact on the statistical analysis of the study. They concern criteria and disease characteristics that are critical to define the study population and criteria that determine or influence clinical endpoints or criteria that may cause immediate hazard to the subjects (impact on subjects' rights, safety or well-being) or increase the risk to subjects.

The list of (potentially) major protocol deviations will be reviewed by the sponsor and finalized prior to database lock. Detailed information can be found in the trial protocol deviation criteria list.

Major protocol deviations will be tabulated according to their category:

- Selection criteria not met
- Subject not withdrawn as per protocol
- Prohibited concomitant medication
- Treatment non-compliance
- Efficacy assessment deviation
- Other

Additionally, major protocol deviations will be listed including categorization and description. Violation to the in- and exclusion criteria will also be listed separately.

Subjects with major protocol deviations will be excluded from all analyses performed on the PP Population.

A detailed list of tables and listings can be found in Section 14.1 and Section 16.1, respectively.

5.3 Demographic and Other Baseline Characteristics

Demographic data and baseline disease characteristics will be evaluated descriptively using standard statistical tools, including mean, standard deviation, median, minimum and maximum for continuous variables and counts and percentages for categorical variables. Summaries will be presented by treatment group and overall on the ITT population. The following demographic parameters and baseline disease characteristics will be included in the tables and/or listings:

Demographic parameters:

- Gender at birth: male / female
- Age at the moment of signing the ICF (years): the age is not recalculated when already available in the database. If not available, it will be calculated as (date of screening – date of birth) / 365.25 and rounded to integer.
- Year of birth: only listed
- Date of signing the ICF: only listed
- Race: not allowed to ask / white / black or African American / Asian / American Indian or Alaska native / native Hawaiian or other Pacific islander / other
Specifications for Asian and other race: only listed
- Ethnicity: not allowed to ask / Hispanic or Latino / non-Hispanic or non-Latino
- Height (cm)
- Weight (kg)
- Blood group
- Body mass index BMI = (weight in kg) / (height in m)² (kg/m²): the BMI will be recalculated and rounded to 1 decimal, even when already available in the database. The original BMI will not be listed in that case.

Baseline disease characteristics:

- Time since TTP diagnosis (years) = (date of screening visit – date of TTP diagnosis)/365.25. For the calculation of time since TTP diagnosis, partially missing start dates will be imputed as follows:
 - Missing day will be imputed by 15
 - Missing day and month will be imputed by 1JUL
 - Note: If the start date would come later than the randomization date after imputation following this rule, the start date will be imputed with the randomization date instead.
- ADAMTS13 activity at admission or baseline: <10% / ≥10%
Note: The smallest value of ADAMTS13 activity at admission, as measured by a local laboratory – if available – and ADAMTS13 activity at baseline will be used for this summary, as ADAMTS13 activity levels can be substantially impacted by the prior PE.

- Previous TTP episode(s): initial / recurrent
- Number of previous TTP episodes: 0 / 1 / 2 / >2
- GCS at randomization: ≤12 / 13-15
- Baseline organ damage markers: LDH, cTnI and serum creatinine
- Baseline organ damage marker categories (LDH, cTnI, serum creatinine): <=ULN / >ULN
- Baseline platelet count. This parameter is assessed by a local laboratory.
- Baseline SMMSE total score
- Baseline RICO activity, vWF:Ag concentration and FVIII:C activity
- Baseline complement factors C5a and C5b-9
- Severity of disease at baseline category: very severe / less severe. Very severe is defined as French severity score ≥ 3 **or** severe neurological involvement at baseline (i.e., coma, seizures, focal deficit) **or** cardiac involvement (cTnI $> 2.5 \times$ ULN). The French severity score (Benhamou, 2012) is a discrete score from 0 to 4, involving evaluation of three parameters: cerebral involvement: yes = 1 / no = 0, LDH: $>10 \times$ ULN = 1 / $\leq 10 \times$ ULN = 0, age: >60 years = 2 / >40 and ≤ 60 years = 1 / ≤ 40 years = 0.

A detailed list of tables and listings can be found in Section [14.1](#) and Section [16.1](#), respectively.

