* Of note, the PE administered prior to randomization (PE of unrestricted intensity) may be given prior to signing ICF (as part of standard of care) and may be spread over 2 or more sessions in 24 hours as long as considered part of the 1 intense PE for the treatment of the presenting TTP episode. Note that the maximum time allowed between the start of first PE (i.e., PE administered prior to randomization) and the start of the first PE after randomization (i.e., the first on-study PE) is 24 hours.

neurological symptoms (Glasgow coma scale [GCS]).

Standard of care treatment:

- PE with plasma (e.g., fresh frozen plasma, solvent detergent/viral-inactivated plasma, cryosupernatant) at 1 to 1.5 x estimated plasma volume daily as of randomization. The PE prior to randomization[†] should have been given with volume and intensity at the discretion of the Investigator.
Once the platelet count is $\geq 150 \times 10^9/L$, daily PE should continue for at least 2 days. Tapering of PE after platelet count normalization, defined as reducing its frequency to less than once per day, is strongly discouraged and if considered, should be discussed with the Medical Monitor.
- Corticosteroid treatment should be initiated/continued with (methyl)prednisolone or (methyl)prednisone regimen of at least 1 mg/kg/day intravenous (i.v.) or per orale (p.o.) during the daily PE period and continued for the 1st week after end of daily PE. Afterwards corticosteroids may be tapered at the discretion of the Investigator, with the aim of being corticosteroid-free by Day 30 after cessation of daily PE as clinically indicated. At the Week 3 visit of the 30-day post-daily PE period, corticosteroid tapering should be reassessed based on ADAMTS13 activity data of the previous 2 visits and other clinical signs of underlying disease.
- Other immunosuppressive treatment: The use of other immunosuppressive treatment (e.g., rituximab) is allowed per standard site practice but should be considered in light of protocol required corticosteroid treatment.

Study drug treatment:*Daily PE period[‡]*

- Loading i.v. dose: subjects will receive a single loading dose of 10 mg study drug by i.v. bolus injection from 6 hours to 15 minutes prior to the first PE done after randomization; an i.v. bolus of 10 mg will also be given prior to the 1st PE done for treatment of a first exacerbation or relapse.

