^a General medical history and TTP-specific medical history. The result of an ADAMTS13 activity test performed as per standard of care upon admission will be collected in the eCRF, if available.

^b To be assessed within 2 hours prior to randomization.

^c Bleeding assessment is a clinical assessment of signs and symptoms of bleeding (e.g., petechiae, hematuria, epistaxis, meno-metrorrhagia, bruises) performed by the Investigator.

^d Only for women of childbearing potential. Pregnancy test (urine or blood) will be assessed locally.

^e Samples for platelet count, blood smear and serum creatinine will be assessed by a local laboratory (values of samples taken as part of standard of care can be used, if available).

Ablynx NV	Clinical Trial Protocol ALX0681-C301	
Pharm-Olam Ltd.	Final version 3.0	

Table 2: Time and events schedule: Daily PE period ^a

Study Visit	Day 1 (Baseline)	Day 2	Day 3	Day 4	DAILY from Day 5 to end of daily PE	WEEKLY ^b on Day 8, 15, ... (± 1 day)
Complement C5a and C5b-9 (initial daily PE period only)	x					
Randomization	x					
Study drug administration ^c	x	x	x	x	x	x
Plasma exchange + corticosteroids ^d	x	x	x	x	x	x
Neurologic assessments ^e	x	x	x	x	x	x
SMMSE	x	x	x	x	x	x
Clinically significant TTP event	x	x	x	x	x	x
Bleeding assessment ^f	x	x	x	x	x	x
Physical examination	x					x
Height and weight (initial daily PE period only)	x					
Vital signs ^g	x					x
12-lead ECG ^h	x	x	x	x		
Adverse events						→
Concomitant medication						→
Platelet count ^j	x	x	x	x	x	x
Blood smear ^j	x					
Clinical laboratory analyses ⁱ	x					x
Organ damage markers ^k	x	x	x	x	x	x
ADAMTS13 activity	x					
PK	x	x	x			
PD parameters ^l	x	x	x			
Immunogenicity (ADA) ^m	x					

^a The following guidance with regard to timing of assessments planned at a single visit should be followed: 1) ECG and vital signs should be assessed prior to blood sampling, 2) assessments should be done prior to start of PE (and on Day 1, prior to the i.v. dose administration), and 3) s.c. study drug should be dosed after end of the day's PE.

This time and events schedule is also applicable for open-label caplacizumab in case of a first exacerbation or relapse (relapse during the treatment extension period). Of note, complement (C5a and C5b-9) and height and weight are to be assessed at the initial daily PE period only.

^b All assessments to be done on Day 8, 15,... include assessments done on daily basis plus extra weekly assessments.

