1.1.1. TREATMENT OF TTP

Plasma exchange therapy is the standard of care treatment for acquired TTP. It replenishes ADAMTS13, partially normalizing vWF processing, and removes pathogenic auto antibodies when present. Immunosuppressive treatment, most commonly corticosteroids, is started together with the PE therapy. Daily PE therapy is stopped (or tapered) when the platelet count has normalized for at least 48 hours. An "exacerbation" occurs in approximately 30% of patients [17]. Despite prompt initiation of daily PE and immunosuppressive treatment, acquired TTP still has an associated mortality of 10 to 20%. Severe ADAMTS13 deficiency (<10%) has been recognized as a potential biomarker for the management and follow-up relating to risk of relapse of acquired TTP patients [18, 19]. Although different thresholds for defining a severe deficiency in ADAMTS13 activity have been described, recent guidance papers have proposed a cut-off level of <10% to define a severe ADAMTS13 deficiency. ADAMTS13 levels below 10% during remission may predict an increased risk for relapse [20-22] and may be used as marker for active underlying disease [23].

In spite of recent advances in understanding the disease, there are no approved pharmacological therapies for acquired TTP. Caplacizumab represents a novel approach to the treatment microvascular thrombosis inherent in TTP and may provide significant benefit in terms of efficacy, safety and quality of life for subjects with TTP. Caplacizumab is being developed with the aim of preventing platelet consumption and formation of further microthrombi thereby reducing the duration of tissue ischemia and protecting the patient from the manifestations of the disease while the underlying process resolves.

[figure not shown]

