3.2.1. INCLUSION CRITERIA

Each potential subject must satisfy all of the following criteria to be enrolled in the study:

1. Adult male or female ≥ 18 years of age at the time of signing the informed consent form (ICF)
2. Clinical diagnosis of acquired TTP (initial or recurrent), which includes thrombocytopenia and microscopic evidence of red blood cell fragmentation (e.g. schistocytes)
3. Requires initiation of daily PE treatment and has received 1 PE treatment^{§§} prior to randomization
4. Female subjects of childbearing potential (excluding postmenopausal women, sterilized, ovariectomized and hysterectomized women) must have a negative pregnancy test and must agree to use a generally accepted adequate contraceptive method from screening until at least 2 months after last dosing
5. Subjects have provided informed consent prior to initiation of any study specific activity/procedure. In case the subject is unconscious or if their ability to give (written) informed consent is compromised due to the neurological impairment or severity of TTP symptoms, a subject's legal acceptable representative or independent physician (as per local law and Ethics Committee [EC]/Institutional Review Board [IRB] approval) has provided informed consent prior to any study specific activity/procedure.

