4.3 Key Definitions and Labels

4.3.1 Definition of baseline

Baseline is defined as the last non-missing assessment before first administration of study drug.

For assessments with multiple parameters per subject (such as laboratory assessments), baseline will be determined per parameter individually. It is recognized that baseline assessments may thus come from more than one assessment and not just from the “baseline visit” assessment. Baseline will be calculated for each treatment period separately (double-blind treatment and open-label treatment). The assessment on Day 1 of the open-label treatment period, taken before first administration of open-label caplacizumab, will be taken as baseline value for the open-label part.

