6.3 Subgroup analyses

A KM analysis of time to platelet count response (primary endpoint) in function of treatment group (Caplacizumab, Placebo) will be performed separately for the following subgroups:

- ADAMTS13 activity at admission or baseline: < 10% / ≥ 10%
- Previous TTP episode(s): initial / recurrent
- Severity of disease at baseline category: very severe / less severe

Each subgroup analysis will only be conducted if at least 5 data points are available by subgroup in each treatment group.

[figure not shown]
The number and proportion of subjects with refractory TTP by treatment group (Caplacizumab, Placebo) will be summarized for the following subgroups:

- ADAMTS13 activity at admission or baseline: < 10% / \geq 10%
- Previous TTP episode(s): initial / recurrent
- Severity of disease at baseline category: very severe / less severe

The number and proportion of subjects with recurrence by treatment group (Caplacizumab, Placebo, OL Caplacizumab) in the overall treatment period and in the overall study period will be summarized by severity of disease at baseline category (very severe / less severe).

The number and proportion of subjects with at least one treatment-emergent major thromboembolic event, confirmed after adjudication, by treatment group (Caplacizumab, Placebo, OL Caplacizumab) in the overall treatment period will be summarized by severity of disease at baseline category (very severe / less severe).

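### With no admission ADAMTS13 value, a subject is classed on a sample drawn after plasma exchange, so a severely deficient subject can be labelled ≥10%

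*SAP*

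**What the plan says.** **Entry.** Protocol 3.2.1, criterion 3, reads "Requires initiation of daily PE treatment and has received 1 PE treatment" and places that exchange before randomization. The protocol does not fix its size: it "should have been given with volume and intensity at the discretion of the Investigator" (Schedules of Assessments, Table 2 footnote d).

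**Samples.** ADAMTS13 activity is scheduled on Day 1. Table 2 footnote a says that "assessments should be done prior to start of PE (and on Day 1, prior to the i.v. dose administration"). SAP 4.3.1 adds: "Baseline is defined as the last non-missing assessment before first administration of study drug". An earlier, local result may also exist: "The result of an ADAMTS13 activity test performed as per standard of care upon admission will be collected in the eCRF, if available" (Table 1 footnote a).

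**Classification.** SAP 5.3 uses two classes, below 10% and at least 10%. The smaller of the local admission value, if there is one, "and ADAMTS13 activity at baseline will be used for this summary, as ADAMTS13 activity levels can be substantially impacted by the prior PE".

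**Use.** The classes appear in the baseline table (Table 14.1.2.2). They also define a subgroup in SAP 6.3 ("ADAMTS13 activity at admission or baseline: < 10" percent, against 10 percent or more) for the Kaplan-Meier display of time to platelet count response and for the refractory-TTP table. The only stated guard on the time-to-response subgroups is a minimum of 5 data points per subgroup in each arm.

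**The concern.** ADAMTS13 deficiency is not an entry criterion; Protocol 1.1 says it is not needed for the clinical diagnosis. Subjects with activity truly at or above 10% can therefore be enrolled, and a reader will look to the ≥10% subgroup to see how they fared. That reading is only as good as the label.

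The SAP recognises that the earlier PE distorts the Day 1 value and answers by taking the smaller of two values. Where the admission result is absent there is only one value, and it is the distorted one. No undetermined class, exclusion or sensitivity display is planned for these subjects, and SAP 12.1 does not mention them.

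The SAP treats a parallel problem differently. In 9.1.1.1 it declines to state pre-dose status for pre-existing antibodies because every patient has had one PE and no pre-PE sample exists. That section also provides inconclusive and missing classes.

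If the treatment effect differs by deficiency, deficient subjects in the ≥10% group pull its result toward that of the <10% group and blur the contrast the subgroup is meant to show.

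**Working it through.** The plan states no figure on this point, so there is nothing to reproduce. The check is a trace of the rule, followed by an illustration of size.

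**1. Timing.** The required PE precedes randomization. The Day 1 sample precedes the i.v. dose and the first on-study PE. By the schedule the sample therefore falls between the two exchanges, whose starts may be at most 24 hours apart (Protocol 3.3.6).

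**2. Direction.** Protocol 1.1.1 says of PE: "It replenishes ADAMTS13, partially normalizing vWF processing, and removes pathogenic auto antibodies when present". The PE effect on the reading is upward.

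**3. Tracing the rule.**

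| Admission value | Post-PE baseline | SAP 5.3 class | Can PE have hidden a deficiency? |
|---|---|---|---|
| <10% | any | <10% | No |
| any or none | <10% | <10% | No |
| ≥10%, drawn before the first PE | ≥10% | ≥10% | No |
| ≥10%, drawn after plasma was started | ≥10% | ≥10% | Yes |
| none | ≥10% | ≥10% | Yes |

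The fourth row is possible because neither document requires the admission sample to precede plasma. The PE-related error only moves deficient subjects into the ≥10% class.

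**4. Size, on assumptions.** N = 132 comes from SAP 3.2. The other inputs are assumed:

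- π, the true share below 10%: 0.7 to 0.9
- m, the share with no admission value: 0.1 to 0.5
- q, the chance that a truly deficient subject reads ≥10% after PE: 0.1 to 0.5

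Available admission values are taken to classify correctly.

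Misclassified = N·π·m·q. True ≥10% = N·(1 − π). Share of the ≥10% group = misclassified ÷ (misclassified + true ≥10%).

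| π, m, q | Misclassified | True ≥10% | Share |
|---|---|---|---|
| 0.7, 0.1, 0.1 | 132×0.7×0.1×0.1 = 0.9 | 132×0.3 = 39.6 | 0.9/40.5 = 2.3% |
| 0.8, 0.3, 0.25 | 132×0.8×0.3×0.25 = 7.9 | 132×0.2 = 26.4 | 7.9/34.3 = 23% |
| 0.9, 0.5, 0.5 | 132×0.9×0.5×0.5 = 29.7 | 132×0.1 = 13.2 | 29.7/42.9 = 69% |

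**5. What a stricter class would leave.** Confirmed ≥10% = N·(1 − π)·(1 − m), if every available admission sample is pre-PE, m is the same in both groups and the arms split evenly:

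- π = 0.7, m = 0.1: 39.6×0.9 = 35.6, or 17.8 per arm
- π = 0.8, m = 0.3: 26.4×0.7 = 18.5, or 9.2 per arm
- π = 0.9, m = 0.5: 13.2×0.5 = 6.6, or 3.3 per arm, below the minimum of 5

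**The case against.** The SAP has already seen the problem and reduced it. The smaller-value rule protects every subject with an admission result below 10%. Admission results are collected retrospectively, and Listing 16.2.2.5 shows admission and baseline values with date and time, so a careful reader could find the subjects classed on baseline alone. The class label is literal: it describes measured activity at admission or baseline and does not call the ≥10% group non-deficient. The subgroup outputs are descriptive (event counts and quartiles with confidence intervals, or a frequency table), with no subgroup p-value or interaction test planned. All of this stands. It narrows the gap and lowers the stakes, but a listing does not correct a summary table.

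Several stronger readings are tempting and are not supported:

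- **All subjects without an admission value land in ≥10%.** They do not; the post-PE reading decides, and one below 10% is correctly classed.
- **The rule undercounts confirmed deficiency.** The <10% class is every subject with any value below 10%, and the proposed fix leaves that set unchanged. Some truly deficient subjects are missed, but the data cannot confirm them under either scheme.
- **This is the only laboratory check on enrolment.** Entry also requires red-cell fragmentation on microscopy and applies platelet and creatinine limits (Protocol 3.2.1 and 3.2.2).
- **Misclassified subjects could be what triggers the subgroup analysis.** Over the assumed range, true ≥10% subjects alone number 13.2 to 39.6, or 6.6 to 19.8 per arm, so the expected count reaches 5 without them.

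**Conclusion.** The gap is real and limited. Following SAP 5.3 exactly can put a severely deficient subject in the ≥10% class when there is no admission value, or when the admission sample was itself drawn after plasma. The affected outputs are Table 14.1.2.2 and the two ADAMTS13 subgroup displays in SAP 6.3. If proportional hazards fails, SAP 6.1.1 would also explore baseline ADAMTS13 levels as a possible confounder, and the same caution would apply there.

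A reader might infer that the trial's main conclusions are at risk. They are not: the stratified log-rank test uses only the GCS stratum, and the key secondary hierarchy does not use this variable.

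The size cannot be derived from the documents, which give neither the share of missing admission values nor the size of the PE effect. The range of about 1 to 30 subjects, or 2% to 69% of the ≥10% group, rests wholly on the assumed π, m and q. It shows that the mixing could be trivial or dominant; no single percentage should be quoted as an estimate. This is a worthwhile and inexpensive improvement to descriptive output.

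**What to change.** In SAP 5.3 and 6.3, replace the two classes with three:

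1. **<10%:** any admission or baseline value below 10%.
2. **≥10% confirmed:** an admission value of at least 10% from a sample timed before the start of the first PE, and a baseline value that is not below 10%.
3. **Undetermined:** post-PE value or values of at least 10% only. An admission sample that cannot be shown to precede the first PE belongs here.

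Report the count in each class by arm in Table 14.1.2.2. Run the SAP 6.3 displays on class 1 against class 2, and apply the 5-data-point rule to those classes. Keep the current two-way split as a sensitivity display.

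The cost is SAP wording and programming. The ADAMTS13 values with date and time are already planned for Listing 16.2.2.5. The start time of the pre-randomization PE is also needed; the 24-hour limit between PE starts already depends on it, but its presence in the eCRF should be confirmed. The drawback is a smaller ≥10% subgroup, which may fall below 5 per arm and then not be analysed. In that case the class counts would show readers why.
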